4.4.3. ECG

Electrocardiogram (ECG) parameters include heart rate, RR interval, PR interval, QT interval, QRS interval, QTcF intervals. Change from baseline to each post-baseline visit will be calculated. For a summary of ECG parameters, both the single 12-lead ECG data and the ECG triplicate assessments on Day 1 of Cycle 1 and Cycle 2 will be included. For the ECG triplicate assessments at a timepoint, the average of the triplicate assessment will be derived to represent the assessment at the timepoint. An overall ECG interpretation include the following categories: Abnormal, clinically significant; Abnormal, not clinically significant ; Normal; and Unknown.

Potentially clinically significant ECG findings will be identified using the criteria which are included in [Table 9](#).

Additionally, the minimum, and maximum values for each patient over the entire treatment period for each ECG parameter will also be derived. The change from baseline will also be calculated using these minimum and maximum values.

Table 9 Potentially Clinically Significant Criteria for ECG

ECG Parameter (unit)	Criterion value
Heart Rate (bpm)	>120

ECG Parameter (unit)	Criterion value
	<50
PR Interval (ms)	≥ 210
RR Interval (ms)	> 1200
	< 500
QRS Interval (ms)	≥ 120
	≤ 50
QT Interval (ms)	≥ 500
	≤ 300
QTcF (ms)	> 450
	> 480
	> 500
	≤ 300
	Increase from baseline > 30
	Increase from baseline > 60
	> 450 and increase from baseline > 30
	> 450 and increase from baseline > 60
	> 480 and increase from baseline > 30
	> 480 and increase from baseline > 60
	> 500 and increase from baseline > 30
	> 500 and increase from baseline > 60

4.4.4. Vital Signs

Vital signs include systolic blood pressure, diastolic blood pressure, respiratory rate, heart rate, body temperature, weight, Body Mass Index (BMI) will be computed as $\text{weight (kg)} / [\text{height (m)}]^2$.

For vital signs, change from baseline to each post-baseline visit and timepoint will be calculated.

The potentially clinically significant findings of vital signs will also be defined based on criteria defined in [Table 10](#).

Additionally, the minimum, and maximum values for each patient over the entire treatment period for each vital sign parameter will also be derived. The change from baseline will be calculated using these minimum and maximum values.

Table 10 Potentially Clinically Significant Criteria for Vital Signs

Vital Sign Parameter	Criterion value
SBP (mmHg)	≥ 160 ≥ 180 ≤ 90 ≥ 180 and an increase ≥ 20 from baseline
DBP (mmHg)	≥ 105 ≤ 50 ≥ 105 and an increase ≥ 15 from baseline
Temperature ($^{\circ}\text{C}$)	≥ 38.5 ≤ 35.5
Pulse rate (beats/min)	≥ 120 ≤ 50

Vital signs are listed by patient and visit.

4.4.5. Performance Status

ECOG performance status is to be summarized descriptively using counts and percentages by visit. In addition to the collected ECOG score during a Cycle, the maximum post-baseline value for a patient will be derived; both scheduled and unscheduled assessments will be used to identify the maximum post-baseline values.

4.4.6. Echocardiogram

ECHOs are performed at Screening, cycle 2 day 1, cycle 3 day 1, and then on day 1 of every odd cycle thereafter. Assessment parameters include left ventricular ejection fraction and overall interpretation of cardiac function. MUGAs are permitted if ECHOs cannot be performed.

4.4.7. Physical Examination

A comprehensive physical examination at Screening includes patient general appearance, eyes, ears, nose and throat, head and neck, respiratory, cardiovascular, abdomen (gastrointestinal), skin, mucous membranes, genitourinary system, lymph nodes, musculoskeletal, neurological, renal assessments.

Limited physical examination at scheduled visits is a subset the comprehensive physical examination as deemed appropriate by the investigator.

Results of physical examination are listed by patient and visit.

4.4.8. Ophthalmologic Assessments

Ophthalmologic assessments, including eye appearance, slit lamp examination, best corrected visual acuity, visual field, eye movement, pupil reflex, optical coherence tomography, and intraocular pressure, will be performed during the study according to the study schedule of assessments. If the subject has undergone the relevant examinations 60 days before the start of IP

treatment (C1D1), they need not be repeated. Other ophthalmic examinations are to be performed when clinically indicated. If the subject develops an ophthalmic adverse event (AE) related to HMPL-306, the frequency of the examination should be increased to once every cycle until the AE is relieved or stable.

5.1.2. Handling Missing Data

In general, the observed case (OC) data for a visit will consist of the actual observations recorded for the visit. If missing, the OC data will remain missing — no missing imputation will be performed. Safety analyses will be conducted on the OC data only.

However, imputation of missing AE and concomitant medication onset and stop dates will be used to determine the status of each AE and the prior/concomitant status of each medication. The specific imputation rules are provided below, refer to Section [5.1.2.1](#) for the method of imputation of missing AE onset and stop date and Section [5.1.2.2](#) for the method of imputation of missing concomitant onset and stop dates. However, the imputed dates should not be shown in listings.

For demographic and baseline characteristics, each variable will be analyzed and/or summarized using the available data. Unless otherwise specified, patients with missing data will be excluded only from analyses for which data are not available.

5.1.2.1. Adverse Events Start/End Date

AEs with onset/end dates that are partially/completely missing will be imputed as follows.

(i) AE start date:

- If the AE onset date is completely missing, the AE start date will be imputed as the reference start date;
- If the AE onset date is partial missing, then
 - If both the year and the month are available and the year and the month are the corresponding year and month of the reference start date, then the AE start date will be imputed as the reference start date;
 - If both the year and the month are available and the year and the month are not equal to the corresponding year and month of the reference start date, then the AE start date will be imputed as the 1st day of the month;
 - If only the year is available and the available year is the corresponding year of the reference start date, then the AE start date will be imputed as the reference start date;
 - If only the year is available, and the available year is not equal to the corresponding year of the reference start date, then the AE start date will be imputed as the January 1st of the year

(ii) AE end date will be imputed as below for the partial date only, the imputation rules only apply when the AE is not ongoing:

- If both the year and the month are available, AE end date will be imputed as the last day of the month;
- If only the year is available, AE end date will be imputed as the December 31st of the year.

If the imputed AE end date is after the death date for patients is know to be dead at end of study or cut off date, the date of the death will be used for AE end date. If the imputed AE end date is after the last known alive date for patients alive at the end of study or cut off date, the date of last known alive date will be use for AE end date.

For AE continuing at the cut-off date, the end date will not be imputed and instead will be reported as “ongoing”.

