4. ENDPOINTS

4.1. General Principles for Derived and Transformed Data

4.1.1. Reference Start Date and End Date and Study Day

Reference start date is defined as the first date when a non-zero dose of study drug was administrated (first administration/dose date). Day 1 is the day of the first dose of study treatment in Cycle 1.

Study day will be calculated from the reference start date, and it will be used to show start/stop day of assessments and events relative to the first administration of study treatment.

- If the date of the event is on or after the reference start date, Study day = (date of event – reference start date) + 1.
- If the date of the event is prior to the reference start date, Study day = (date of event – reference start date).

In the situation where the event date is partial or missing, the date will appear partial or missing in the listings.

Reference end date is defined as the last date when a non-zero dose of study drug was administered.

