4.4.1. Adverse Events (AEs)

All AEs will be coded from verbatim text to preferred term (PTs) and grouped by system organ class (SOC) using the Medical Dictionary for Regulatory Activities (MedDRA) version 27.1. AEs will be graded by investigator according to NCI CTCAE v5.0. Missing severity grade will not be imputed.

An AE is considered a TEAE:

(i) If one of the criteria is met:

1. If the onset date is on or after the start of study treatment until 30 days after the last dose or prior to the start of a subsequent anti-tumor therapy (whichever comes first), or if the onset date is missing; or
2. If the AE has an onset date before the start of study treatment, but worsened in severity after the study drug administration (i.e. SAE start date is on or after the start of study treatment until 30 days after the last dose or prior to the start of a subsequent anti-tumor therapy (whichever comes first));

(ii) Beyond 30 days after the last dose or after the start of a subsequent anti-tumor therapy (whichever comes first), treatment-related SAEs will also be considered as TEAEs.

Investigator assessed AEs causality to study drug will be classified as "Related" and "Not Related". An AE with a missing causality will be classified as "Related" to study drug.

Other AE variables include drug-related AEs, COVID-19 related AEs, AEs leading to study drug modifications (i.e. dose interruption, dose reduction, or study drug withdrawal), AEs leading to death, and SAEs.

For AEs which are not on-going, duration of AE (days) is defined as AE end date – AE start date +1; for on-going AEs, the end date will be listed as ‘Ongoing’.

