5.1.2.2. Concomitant Medication/Procedure/Surgery Start/End Date

Concomitant Medication/Procedure/Surgery with onset/end dates that are partially/completely missing will be imputed as follows.

(i) start date:

- 1st day of the month will be used to impute the start date if only the day is missing
- January 1st will be used to impute the start date if both the day and month are missing
- If the date is completely missing, then the day before the reference start date will be imputed as the start date.

(ii) end date:

- Last day of the month will be used to impute the end date if only the day is missing
- December 31st of the year will be used to impute the end date if both the day and month are missing
- If the date is completely missing, assign ‘continuing’ status to the end date

If the imputed start date is after the end date, the start date will be imputed as the end date. If the imputed end date is after the death date or last known alive date, the date of the death or last known alive date will be imputed as the Concomitant medication/procedure/surgery end date.

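### SAP 5.1.2.1 moves a missing or matching partial AE start to the first-dose date without checking the AE end date, so an event that ended before dosing is counted as a TEAE

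*SAP*

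**What the plan says.** **How the start date is imputed (SAP 5.1.2.1).** There are two matching branches for a partial start. The first opens with the condition "If both the year and the month are available and the year and the month are the corresponding year and month of the reference start" (that is, of first dose), and its outcome is "then the AE start date will be imputed as the reference start date". The second, "If only the year is available and the available year is the corresponding year of the reference start date, then the AE start date will", has the same outcome. A completely missing start also becomes the reference start date. SAP 4.1.1 fixes that date: "Reference start date is defined as the first date when a non-zero dose of study drug was administrated".

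**What is checked.** The only bounds in SAP 5.1.2.1 apply to an imputed end date. It is cut back to the date of death, or, "If the imputed AE end date is after the last known alive date for patients alive at the end of study or cut off date", to the last date the patient was known to be alive. The imputed start is never compared with the end.

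**How a TEAE is defined (SAP 4.4.1).** The main criterion is "If the onset date is on or after the start of study treatment until 30 days after the last dose" (or until a new anti-tumor therapy, if sooner), with the alternative "or if the onset date is missing". Neither part refers to the AE end date. The same section defines the duration of an AE that is not ongoing as end minus start plus one day.

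**The parallel rule (SAP 5.1.2.2).** For concomitant medications, procedures and surgery, the SAP does compare the two dates: "If the imputed start date is after the end date, the start date will be imputed as the end date".

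**What imputed dates are for (SAP 5.1.2).** They serve to settle the status of each AE, and they are kept out of the listings.

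**The concern.** Placing an uncertain onset on the day of first dose is a sound conservative default when the timing really is unknown. It is not sound when the record shows that the event was over before the first tablet was taken. The rule then overrides a fact in the database and produces a start later than the end.

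The consequence is a false TEAE. TEAE incidence is part of the primary safety endpoint (SAP 2.1, Table 1), and it is tabulated by dose level, where cohorts are small. SAP 4.4.1 also treats a missing causality as related, so a pre-dose event with no causality entry could appear as a treatment-related TEAE. Because imputed dates are not listed, someone reading the listings would not see why the event was counted.

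**Working it through.** **Inputs**

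- Imputation branches: SAP 5.1.2.1. TEAE rule and duration formula: SAP 4.4.1. Reference date: SAP 4.1.1.
- Collection of AEs from main consent: Protocol 8.2.1. Screening of up to 28 days before Cycle 1 Day 1: Protocol 6.1.2. The protocol supplied is Amendment 2, whereas the SAP cites Amendment 3; I assume these two provisions did not change.
- First dose on 20 June 2022: an assumed example.

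The plan gives no figure of its own to reproduce.

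**Rules as written, applied to example records**

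The last column assumes that imputed dates enter the duration formula.

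| Start recorded | End recorded | Start used | End used | TEAE? | End − start + 1 (days) |
|---|---|---|---|---|---|
| June 2022 | 12 June | 20 June | 12 June | yes | 12 − 20 + 1 = −7 |
| June 2022 | 18 June | 20 June | 18 June | yes | 18 − 20 + 1 = −1 |
| June 2022 | 19 June | 20 June | 19 June | yes | 19 − 20 + 1 = 0 |
| 2022 | 30 May | 20 June | 30 May | yes | −21 + 1 = −20 |
| 2022 | May 2022 | 20 June | 31 May (imputed) | yes | −20 + 1 = −19 |
| missing | 12 June | 20 June | 12 June | yes | −7 |
| June 2022 | June 2022 | 20 June | 30 June (imputed) | yes | 11 |
| May 2022 | 12 June | 1 May | 12 June | no | 43 |

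The first six records are wrong: each event ended before dosing and is still a TEAE. The fifth shows that an imputed end date can cause the conflict as well as a recorded one. The last two contain no contradiction.

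**General form.** If the end date is k days before first dose and the start is set to first dose, duration = −k + 1 = 1 − k. That is 0 for k = 1, −1 for k = 2, and 1 − 28 = −27 for k = 28, the full length of screening.

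**With the check from SAP 5.1.2.2 added.** The start used becomes the earlier of the imputed start and the end date. In the first five records the start equals the end, the event is not a TEAE, and the duration is 1 day. The sixth record also gets a start of 12 June, but the missing-onset clause in SAP 4.4.1 would still make it a TEAE, so that clause needs its own change. The last two records are unaffected.

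**Size of one miscount.** In a cohort of 3 (the minimum in Protocol 4.1.1), one false TEAE moves a preferred term from 0/3 = 0% to 1/3 = 33%. Across the 27 to 36 patients foreseen in SAP 2.3.1, it adds between 1/36 = 2.8% and 1/27 = 3.7%.

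**The case against.** Several points can fairly be made for the plan.

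- **Negative durations.** A reader might infer that the SAP will report impossible durations. The documents do not establish this. SAP 5.1.2 gives imputed AE dates one stated purpose, AE status, and otherwise confines safety analyses to observed data; SAP 4.1.1 leaves partial dates partial in listings. On that reading an AE with a partial start simply has no duration. Even on the other reading, the only planned duration summary is for AEs of special interest, with a single category, abnormal hepatic function (SAP 5.2.11.2). This objection stands, so the duration result is conditional.
- **Frequency.** A reader might infer that such records are to be expected. The protocol shows only that pre-dose AEs are collected, not that they carry incomplete start dates. Conditions present at screening go to medical history unless they worsen (Protocol 8.7.5). Three things must coincide: a missing or matching partial start, a usable end date, and an end before first dose. This stands too; the count could be zero.
- **Dose finding.** A reader might infer that the MTD or RP2D is affected. Nothing shows this. Escalation rests on DLTs, and the DLT-evaluable set comes from committee review (SAP 3.1.3 and Section 7), not from date imputation.
- **Deliberate caution.** Counting a missing onset as treatment-emergent is an explicit choice in SAP 4.4.1, and it errs toward over-reporting. That is reasonable where timing is unknown. It does not answer the case where the end date shows that the event was over before dosing.

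What survives is the misclassification, which follows from the stated rules and is corrected nowhere else in the documents.

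**Conclusion.** The AE start-date rule is wrong as written, within a narrow scope. An AE with a missing start, or a partial start matching the month or year of first dose, and with a recorded or imputed end before first dose, is classified as a TEAE although it cannot have started on treatment. The comparison made in SAP 5.1.2.2 suggests an oversight rather than a chosen convention.

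The misclassification needs no further assumption about analysis practice, because SAP 5.1.2 says that imputed dates decide AE status. The zero or negative duration of 1 − k days does need one, namely that imputed dates enter the duration formula. The number of affected records is not in the documents and is probably small. The effect is on descriptive TEAE tables, with no hypothesis test involved and no demonstrated effect on dose decisions. This is a minor point, worth correcting because the correction is so cheap.

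**What to change.** 1. In SAP 5.1.2.1, add the check that SAP 5.1.2.2 already has: where the imputed AE start falls after the AE end date, whether that end is recorded or imputed, set the start to the end date.
2. In SAP 4.4.1, limit the missing-onset clause to AEs whose end date is not before first dose, and state that an AE ending before first dose is not a TEAE. Without this, a completely missing onset would remain a TEAE despite edit 1.
3. State whether AE duration, AESI duration and time to AESI onset use imputed dates. This matters even after edit 1, because the one-day duration of a capped record is a product of the rule and not an observation.

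The cost is a few SAP sentences and a small programming change, with no new data. AEs ending on or after first dose keep their present classification. If the database is already locked, the change can be recorded in the clinical study report, as SAP Section 1 provides for deviations.

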5.1.2.2. Concomitant Medication/Procedure/Surgery Start/End Date

Concomitant Medication/Procedure/Surgery with onset/end dates that are partially/completely missing will be imputed as follows.

(i) start date:

- 1st day of the month will be used to impute the start date if only the day is missing
- January 1st will be used to impute the start date if both the day and month are missing
- If the date is completely missing, then the day before the reference start date will be imputed as the start date.

(ii) end date:

- Last day of the month will be used to impute the end date if only the day is missing
- December 31st of the year will be used to impute the end date if both the day and month are missing
- If the date is completely missing, assign ‘continuing’ status to the end date

If the imputed start date is after the end date, the start date will be imputed as the end date. If the imputed end date is after the death date or last known alive date, the date of the death or last known alive date will be imputed as the Concomitant medication/procedure/surgery end date.

5.1.2.3. Date of Death

When a partial death date is reported, below rules will be used:

- If only the day of the month is missing, then date of death will be imputed as 1st of the month.

If the imputed date of death is earlier than EOS date, then date of death will be replaced by EOS date.

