6.1.21 End of Study

The end of the study is defined as the date on which all subjects have their last visit or 1 year after the last subject has their first visit, whichever comes first.

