5.1.2.4. The Last Dose Date of Study Drug

When a partial last dose date of study drug is reported, below rules will be used:

- If only the day of the month is missing, then it will be imputed as the last day of the month;
- If both the day and the month are missing, then it will be imputed as the December 31st of the year
- If the imputed last dose date of study drug is later than date of death (if the subject died) / last known alive date (if the subject is not known to die) / EOT date / EOS date, data cut off date, then it will be replaced by the earliest of the above.

If the last dose date of study drug is complete missing, then it will be imputed by the earliest of the above.

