5.2.11. Safety Analyses

Safety data during the treatment period will be summarized. Treatment period is defined as the duration from the date of the first study drug administration until 30+7 days (7-day window only applies to parameters collected by visit) or prior to the start of a subsequent anti-tumor therapy (whichever comes first) after last study drug administration.

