5.2.11.3. Death

Number of deaths and primary cause of death are summarized descriptively. Similarly, the deaths happening during the treatment period and follow-up period will also be tabulated.

Data of deaths will be provided as patient list in which the on-treatment death will be flagged.

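### A death with unknown day takes the EOS date whenever that is later, with no cap at the end of the reported month, so the imputed date can contradict the record and lose an on-treatment flag

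*SAP*

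**What the plan says.** SAP 5.1.2.3 handles a partial death date in two steps. First: "If only the day of the month is missing, then date of death will be imputed as 1st of the month". Then: "If the imputed date of death is earlier than EOS date, then date of death will be replaced by EOS date". No upper limit follows.

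EOS is not in the SAP's abbreviation list and is not defined in its text. The protocol (section 6.1.21) gives only a study-level meaning: "The end of the study is defined as the date on which all subjects have their last visit", or one year after the last subject's first visit if that is sooner. SAP 5.1.2.4 instead lists the EOS date among mostly patient-level dates: "if the subject is not known to die) / EOT date / EOS date, data cut off date". There the earliest candidate is taken, so EOS acts as a ceiling. In 5.1.2.3 it acts as a floor.

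The death date is then used in two places.

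- **Safety.** SAP 5.2.11.3 says that "the deaths happening during the treatment period and follow-up period will also be tabulated" and that "Data of deaths will be provided as patient list in which the on-treatment death will be flagged". SAP 5.2.11 sets the window: "Treatment period is defined as the duration from the date of the first study drug administration until 30+7 days" after the last dose, or the start of new anti-tumor therapy if earlier. The extra 7 days apply only to parameters collected by visit.
- **Efficacy.** In SAP Tables 3 and 5, a death without progression is a DoR or PFS event on the date of death (rule 2). A death after two or more missed assessments is censored at the last adequate one (rule 7).

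**The concern.** A floor under an imputed death date is sensible, because a death cannot precede the last evidence that the patient was alive. An EOS date need not be such evidence. It may be a disposition date entered when the site learned of the death, which can be weeks later and in another month. The protocol's schedule makes this plausible. The end-of-treatment visit is nominally within 7 days of the last dose and safety follow-up is 30 days after that visit, so the nominal contact is up to day 7 + 30 = 37. If a death is learned of then and the contact date is entered as EOS, the imputed death lies outside the 30-day window. The documents do not say whether sites record EOS in this way. On the protocol's study-level meaning, nearly every partial death date would move to the end of the study.

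What is at stake is the count of on-treatment deaths in a phase 1 study whose primary endpoints include safety, and secondarily the PFS and DoR dates of the same patients.

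**Working it through.** The plan gives no figure to reproduce. All calendar dates below are assumed, and no new anti-tumor therapy is assumed to start.

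**Rule as a formula.** Imputed death = max(1st of reported month, EOS date).

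**Main example.** Last dose 10 June, death in June with day unknown, EOS 18 July.

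- Possible true death: 10 to 30 June, which is day 0 to 20 after the last dose.
- Imputed death: max(1 June, 18 July) = 18 July. From 10 June this is 20 + 18 = 38 days.
- Error: 38 − 20 = 18 days at least and 38 − 0 = 38 days at most.
- The 30-day window ends on 10 July. Every possible true date is inside it. Day 38 is outside it, and outside 37 days as well.

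**How the result depends on EOS.** Last dose 10 March 2023, so the 30-day window ends on 9 April.

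| Reported month | True range (days after last dose) | EOS date | Imputed day | Within 30 days | Inside reported month |
|---|---|---|---|---|---|
| March | 0 to 21 | 20 March | 10 | yes | yes |
| March | 0 to 21 | 15 April | 36 | no | no |
| March | 0 to 21 | 10 May | 61 | no | no |
| March | 0 to 21 | 2 October | 206 | no | no |
| April | 22 to 51 | 25 March | 22 (1 April kept) | yes | yes |
| April | 22 to 51 | 5 April | 26 | yes | yes |
| April | 22 to 51 | 20 April | 41 | no | yes |
| April | 22 to 51 | 10 May | 61 | no | no |

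The impossible dates are those with EOS after the reported month. In the April row with EOS 20 April, the record itself leaves on-treatment status open, so that result is not a contradiction.

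**PFS.** First dose 4 January 2023, last adequate scan 1 March (relative day 57), no progression, death in April with day unknown. PFS = (event date − first dose + 1)/30.4375.

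- Earliest possible, 1 April: 88/30.4375 = 2.89 months. Latest possible, 30 April: 117/30.4375 = 3.84 months.
- EOS 10 May: 127/30.4375 = 4.17 months, later than any possible true value.
- EOS 5 July: the gap from the scan is 126 days. This meets the threshold in SAP 4.2.1.3 for assessments before relative day 120, 2 × (8 × 7 + 7) = 126. The death is censored at 57/30.4375 = 1.87 months. The latest possible true death is 60 days after the scan and would count as an event. The SAP words this threshold for gaps between assessments; I apply it to the death date, as rule 7 requires.

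**Check of the repair.** In the main example, max(1 June, last known alive date) capped at 30 June lies between 10 and 30 June for any last known alive date from 10 June on. That is day 0 to 20, and the flag is kept.

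**The case against.** The strongest reply is that EOS may simply be the patient's last contact or recorded death date. SAP 5.1.2.4 leans towards a patient-level meaning. On that reading the rule is an ordinary floor, and any change of on-treatment status is legitimate. The SAP also follows protocol Amendment 3, while the protocol at hand is Amendment 2, so a definition may exist there. This stands to the extent that the harm is conditional on EOS falling after the reported month. It does not supply the missing cap.

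Several stronger readings are tempting, and the documents do not support them.

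- **Departure from the SAP's own practice.** A reader might infer that the SAP elsewhere uses the last known alive date as a floor. It uses it as a ceiling (5.1.2.1, 5.1.2.4, 5.1.2.6, and 5.1.2.2: "If the imputed end date is after the death date or last known alive date").
- **Wider loss of safety information.** TEAE status turns on onset date (SAP 4.4.1), so the tables of TEAEs leading to death do not move with the imputed date. Protocol 8.7.8 requires deaths in the AE reporting period to be reported as SAEs. Only the listing flag and the split by period can change.
- **AE end dates shifting generally.** SAP 5.1.2.1 caps only imputed end dates that fall after death. In the main example an AE ending in June would be imputed to 30 June, before 18 July, so the cap is not reached. An end date with the month also missing could reach it.
- **PFS always lengthened.** Censoring under rule 7 can shorten it instead, and deaths after progression do not affect it.

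It is also fair that late deaths may be few. Survival follow-up covers only expansion cohorts A, B and D, and no expansion patient was enrolled.

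**Conclusion.** The point holds, as a minor and conditional one. As written, the rule can give a death date that the record rules out, and in the main example it turns a certain on-treatment death into a follow-up death.

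A reader might take the error there to be up to 47 days (1 June to 18 July). That is only the shift from the first guess. The patient took a dose on 10 June, so the 18 to 38 days shown above is the possible error. A reader might also infer that almost any EOS date causes trouble. An EOS date before the reported month leaves the 1st unchanged, one on or before the true death is a valid floor, and one equal to the death date is correct.

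The conclusion rests on two things that the documents leave open: what EOS date means, and how many death dates lack a day. The second number is not given and may be zero, in which case nothing changes. The study is descriptive with no hypothesis test, so no formal inference is affected.

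**What to change.** Replace the second sentence of SAP 5.1.2.3 with a rule of this kind: *impute the later of the 1st of the reported month and the patient's last known alive date, but no later than the last day of the reported month.* Do not use the EOS date here. The SAP relies on the last known alive date in several sections without defining it, so one line should say which records it is drawn from.

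If the EOS date is kept as a floor, define it at patient level and apply the same month-end cap.

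The cost is one SAP sentence, a short definition and the matching line of derivation code. No further data collection is needed.
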